3.9.2 Adherence to Home BP Measurement

As per Section 8.2.1 in the protocol, adherence to home BP monitoring schedule will be assessed at the randomization visit. In the week before Randomization, at least 6 measures (e.g. ≥ 2 sets of triplicate measures, ≥ 3 sets of duplicate measures) are required including at least 1 morning and 1 evening each with ≥ 2 measures. Morning is defined as any measure in the AM and evening as any measure in the PM. Morning and evening do not have to be same day.

Following Randomization, a minimally valid half-day of BP measurements is defined as one that has either:

- ≥ 1 BP values in the morning (earlier than 12:00 hours), or
- ≥ 1 BP values in the evening (12:00 hours or later)

Study protocol Section 10.2.8 instructs that in the week before Randomization and Week 4 trial visits, BP measurements should be taken on the 4 days immediately prior to the day of on-site trial visit. In other weeks, measurements should be performed on a single day.

Adherence to home BP measurement will be evaluated by looking at the number of minimally valid half-days and will be summarized by counting the number of minimally valid AM and PM periods of BP measurements per week of follow-up, by treatment group and overall.

3.9.3 Protocol Deviations

Over a blind review meeting, before database lock and unblinding, the different protocol deviations will be classified as minor or major and categorized by type (e.g. non-compliance to treatment, prohibited medication etc.) by the clinical teams. The number of major protocol deviations will be summarized by type of deviations. All protocol deviations will be listed.

Major protocol deviation categories include, but are not limited to:

- Randomized even though ineligible (not including minor non-safety related reasons such as miscalculation of run-in adherence)
- Received the wrong treatment
- Non-adherence to study treatment (adherence $< 80\%$ or $> 120\%$), for reasons known to be unrelated to tolerability or efficacy eg. participant moved overseas
- Interruption to study treatment as a result of supply chain issues in which protocol-specified procedures were not followed,
- Insufficient valid home BP measurements for home blood pressure calculation at randomization or follow-up visit 1.

A summary table will present the tabulations by major protocol deviation on the Screened Set. All protocol deviations will be listed.

3.10 Analysis of the Efficacy Endpoints

3.10.1 Estimand

3.10.1.1 Primary Estimand

The population for the primary estimand includes adults (aged ≥ 18 years) with hypertension. The variable of interest is the difference between home measured SBP after Week 4 of treatment post-randomization and the home measured SBP in the week prior to randomization. The primary analysis will be performed on the Randomized Set including all participants who were randomized to treatment.

Intercurrent events for the primary analysis are listed below:

- Received the wrong treatment (i.e. a treatment other than the randomly assigned treatment)
- Discontinuation from the study treatment for reasons related to the study protocol or study treatment, such as lack of efficacy, tolerability, or adverse event.

For the primary analysis, the Treatment Policy Strategy will be applied where intercurrent events that do not result in missing BP measurements are considered irrelevant and data will be analyzed regardless of the occurrence of the event. The use of a Treatment Policy Strategy most closely aligns to an ITT analysis, where all available and imputed data contribute toward the estimated treatment effects. Participants with intercurrent events and missing data will have imputations performed from those participants with intercurrent events and non-missing data (Section 3.10.2.6). Participants without intercurrent events and missing data will have imputations performed from those participants without intercurrent events and non-missing data.

The primary analysis will be performed using a mixed model for repeated measures (MMRM). Sensitivity analyses adjusted for covariates are planned for the primary endpoint (Section 3.10.2.3). Subgroup analyses will also be performed among the primary analysis set (Section 3.10.2.5).

Supplemental analyses will be performed among the following analysis sets:

- 1) Full Analysis Set, including participants who have taken at least 1 dose of study treatment post-randomization and applying imputation methods in the same manner as the primary analysis methods (analysis to be performed if samples differ by $>5\%$)
- 2) Complete cases with Clinic BP Substitution: Participants with missing pre-Randomization or Week 4 home BP assessment with clinic BP recorded will have their clinic measured value substituted for the missing home BP assessment at the respective visit. Any participants with missing Baseline or Week 4 assessments without an in-clinic assessment at the designated visit will be excluded.
- 3) Per Protocol Analysis Set: Excluding any participants with an intercurrent event or major protocol deviation.

3.10.1.2 Secondary Estimand

The population for the secondary estimands includes adults (aged ≥ 18 years) with hypertension. The variables of interest are listed in Section 2.4.1.2.

Hypothesis testing is not planned for secondary endpoints and, therefore, the results of the planned analyses are considered exploratory. Statistical analyses for continuous secondary endpoints will be performed on Complete Cases only. Statistical analyses for binary secondary endpoints will be performed on the Randomized Set, where participants with missing endpoint values will be assumed to have not achieved the endpoint (i.e., missing data will be singly imputed as "failure").

Table 3-1 Estimands

Estimand Label	Treatment Comparison	Population	Population-level summary	Analysis Population	Handling of Intercurrent events
Primary Analysis	GMRx2-dose 1 vs Placebo and GMRx2-dose 2 vs Placebo at week 4	Adults with hypertension	Difference in change in home SBP, for GMRx2 vs Placebo Analysis will be performed using MMRM with Multiple Imputation	Randomized Set	Treatment policy strategy with intercurrent events only used as part of missing data imputation strategy
Primary Estimand, Sensitivity Analysis – Adjusted Analysis	GMRx2-dose 1 vs Placebo and GMRx2-dose 2 vs Placebo at week 4	Adults with hypertension	Difference in change in home SBP, for GMRx2 vs Placebo Analysis will be performed using MMRM with Multiple Imputation, adjusted for covariates	Randomized Set	Treatment policy strategy with intercurrent events only used as part of missing data imputation strategy
Primary Estimand, Sensitivity Analysis – Adjusted Analysis	GMRx2-dose 1 vs Placebo and GMRx2-dose 2 vs Placebo at week 4	Adults with hypertension	Difference in change in home SBP, for GMRx2 vs Placebo Analysis will be performed using MMRM with Multiple Imputation, with interaction terms for specified subgroups	Randomized Set	Treatment policy strategy with intercurrent events only used as part of missing data imputation strategy
Primary Estimand, Supplemental Analysis	GMRx2-dose 1 vs Placebo and GMRx2-dose 2 vs Placebo at week 4	Adults with hypertension	Difference in change in home SBP, for GMRx2 vs Placebo Analysis will be performed using MMRM with Multiple Imputation	Full Analysis Set	Treatment policy strategy with intercurrent events only used as part of missing data imputation strategy
Primary Estimand, Supplemental Analysis	GMRx2-dose 1 vs Placebo and GMRx2-dose 2 vs Placebo at week 4	Adults with hypertension	Difference in change in home SBP, for GMRx2 vs Placebo Analysis will be performed using MMRM with Clinic BP Substitution	Randomized Set, Complete Cases with Clinic BP Substitution	Treatment policy strategy with substitution of missing home BP assessments with clinic BP assessment values

Estimand Label	Treatment Comparison	Population	Population-level summary	Analysis Population	Handling of Intercurrent events
Primary Estimand, Supplemental Analysis	GMRx2-dose 1 vs Placebo and GMRx2-dose 2 vs Placebo at week 4	Adults with hypertension	Difference in change in home SBP, for GMRx2 vs Placebo Analysis will be performed using MMRM	Per Protocol Set	All participants with intercurrent events and major protocol deviations excluded from analysis
Secondary Estimands, Continuous Endpoints	GMRx2-dose 1 vs Placebo and GMRx2-dose 2 vs Placebo at week 4	Adults with hypertension	Continuous Endpoints: Analysis will be performed using MMRM, Summary variable will be LS Means and LS Mean Difference	Randomized Set	Treatment Policy Strategy for intercurrent events with Week 4 results reported. Complete cases only with no imputation for missing data.
Secondary Estimands, Binary Endpoints	GMRx2-dose 1 vs Placebo and GMRx2-dose 2 vs Placebo at week 4	Adults with hypertension	Binary Endpoints: Analysis will be performed using GEE, Summary variable will be Odds Ratios, Risk Difference and corresponding confidence intervals (CIs)	Randomized Set	Treatment Policy Strategy for intercurrent events with results reported. Missing endpoint data will be imputed as "failure".

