3.10.2.4 Adjusted Analyses

Adjusted analyses will be performed as a sensitivity analysis by adding the following covariates: age (continuous), sex, race, BMI category, diabetes and number of treatments at screening. The adjusted treatment effect will be reported as the adjusted least square mean difference and 95% confidence interval.

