3.10.2.5 Subgroup and Additional Analyses

Pre-specified subgroup analyses will be carried out irrespective of whether there is a statistically significant treatment effect on the primary endpoint. Subgroups are defined as follows:

- Sex (Male; Female)
- Age (<55; 55-65; > 65 years)
- Race (black; non-black)
- BMI (<30, >=30 kg/m²),
- Diabetic; non-diabetic,
- Region (USA; Other)
- Placebo run-in single-blinded (yes/no)*
- Baseline (at Randomization) home SBP category (<140, 140-149, ≥150 mmHg) and DBP category (<80, 80-89, ≥90 mmHg)
- Number of BP medications at Screening (0, 1)
- Hypertension status at Screening – office BP <140/90 mmHg, ≥140/90 mmHg; office BP <130/80 mmHg, ≥130/80 mmHg
- Orthostatic (postural) hypotension at Randomization (measured at clinic BP): see [Section 3.10.3.2](#) for definitions.

* UK authorities required unblinded run-in period, non-UK centres had single blinded run-in period.

Subgroup analyses will be performed by inclusion of the subgroup main effect as well as two-way interaction terms as fixed effects with treatment within the MM. Heterogeneity of treatment effect between subgroups will be evaluated using contrast statements, to test whether the LS Mean difference between GMRx2 and placebo group differs between levels of the subgroup. Comparisons will be performed separately for each GMRx2 dose level against placebo. A comparison of combined GMRx2 doses against placebo by subgroups will also be performed. LS Means, LS Mean Differences and 95% CIs will be reported for each category of subgroup. If any subgroup does not have sufficient participants for statistical modelling

(i.e., model convergence), descriptive statistics will be provided. A forest plot will also be provided to visualize the overall subgroup analysis.

Sample SAS Code accounting for Sex as Subgroup:

```
PROC MIXED DATA = ADEFF EMPIRICAL METHOD = REML;
  CLASS SITEID SUBJID VISIT TRTP SEX;
  MODEL AVAL = BASE TRTP|SEX / CL;
  REPEATED / SUBJECT = SITEID TYPE = CS;
  WHERE VISIT IN ('WEEK4');
  LSMEANS TRTP*SEX / DIFF CL ALPHA=0.05;
  lsmeans estimate trtp*sex "(TS11-TS31)-(TS12-TS32)"
    [1, 1 1] [-1, 3 1] [-1, 1 2] [1, 3 2]; *TRTP=1 vs TRTP=3;
  lsmeans estimate trtp*sex "(TS21-TS31)-(TS22-TS32)"
    [1, 2 1] [-1, 3 1] [-1, 2 2] [1, 3 2]; *TRTP=2 vs TRTP=3;
  RUN;
```

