- 4) Participants with missing Week 4 home BP assessments who were adherent to study treatment and did not experience intercurrent events will have their results imputed for the primary analysis using multiple imputation. Participants without intercurrent events will have their missing result based on other participants also without intercurrent events and within the same treatment group.

If there is not a sufficient sample size to perform multiple imputations as described, participants with and without intercurrent events will be included in the source sample for imputation.

Multiple imputation (MI) will be applied, replacing each missing average SBP home assessment with a set of plausible values from the identified subsample, listed above. This will represent the uncertainty of the correct value based on the observed results. The multiply imputed datasets will be analyzed using standard procedures for complete data with their results combined with a variance-adjustment. The multiple imputation will be computed as follows:

- 1) Imputation:
 - a. For missing baseline, a regression method will impute missing data from the overall randomized sample.
 - b. For missing Week 4 SBP results, a regression method will impute missing data from the respective subsample with or without intercurrent events, as specified above and within the respective treatment group. Imputation will be performed using a Fully Conditional Specification (FCS) model using the regression method and will include the following factors:
 - Age, sex, race, BMI and ethnicity
 - Patient smoking and alcohol consumption
 - Baseline (at Randomization) average home SBP
- 2) Analysis: The final multiple imputed datasets will be analyzed using Rubin's Rule.

Proc MI and Proc MIANALYZE in SAS will be used to generate the datasets and run the analyses.

Sample SAS Code:

```
PROC MI DATA = SBP OUT = SBP2 SEED = 20231010 NIMPUTE = 100
  MINIMUM = . . . . . . . . 80  ROUND = . . . . . . . . . . 1
  MAXIMUM = . . . . . . . . 200  MINMAXITER = 5000 SIMPLE NOPRINT;
  FCS REG(BASE = TRTPN AGE SEX RACE BMI ETHNIC SMK ALC/ DETAILS);
  FCS REG(SBP4 = TRTPN AGE SEX RACE BMI ETHNIC SMK ALC BASE / DETAILS);
  CLASS TRTPN SEX RACE ETHNIC SMK ALC;
  VAR TRTPN AGE SEX RACE BMI ETHNIC SMK ALC BASE SBP4;
  RUN;
*SBP2 will be reformatted into an analysis dataset, here titled ADEFF with
each observation on a separate line;
>Note that in actual implementation, the imputations will be done

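### Treatment-by-subgroup tests run on multiply imputed data, but the Week 4 imputation model omits 7 of the 12 subgroup factors, so those interactions shrink toward zero and their tests are conservative

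*SAP*

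**What the plan says.** - **Data used.** SAP Table 3-1 puts the subgroup row on the Randomized Set with imputation: "Analysis will be performed using MMRM with Multiple Imputation, with interaction terms for specified subgroups". The covariate-adjusted row reads the same way: "Analysis will be performed using MMRM with Multiple Imputation, adjusted for covariates".
- **Imputation model.** SAP 3.10.2.6 lists three groups of factors for Week 4 home SBP: "Age, sex, race, BMI and ethnicity"; "Patient smoking and alcohol consumption"; "Baseline (at Randomization) average home SBP". The text says the regression is fitted within treatment group. The sample code has the same covariates: "FCS REG(SBP4 = TRTPN AGE SEX RACE BMI ETHNIC SMK ALC BASE / DETAILS".
- **Who is imputed this way.** Item 4 of 3.10.2.6 covers adherent participants without an intercurrent event, whose donors are similar participants in the same arm. Participants who discontinued for treatment- or procedure-related reasons, and non-adherent participants, are imputed from placebo participants with intercurrent events.
- **Subgroups.** SAP 3.10.2.5 adds treatment-by-subgroup terms and tests, by contrasts, whether the GMRx2-placebo difference varies between levels.
- **Adjusted analysis.** SAP 3.10.2.4 adds "age (continuous), sex, race, BMI category, diabetes and number of treatments at screening" and reports the adjusted treatment difference.
- **Changes to the imputation model.** The only one foreseen is dropping covariates if the model does not converge.

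**The concern.** An imputation model should contain at least the terms that the analysis model will test. Here the analysis asks whether the treatment effect differs by, say, number of BP medications, while the missing values are drawn from a model that does not contain that factor. The drawn values dilute the contrast being tested.

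The error runs in one direction: effects look more uniform across subgroups than the observed data suggest. Some of the omitted factors matter to the plan itself. SAP 3.10.2.5 expects clinical use in people previously on 0 or 1 drugs, and it makes run-in blinding a subgroup because the UK run-in was not blinded. No interaction test on observed values is planned as a cross-check. The supportive analyses in 3.10.2.2 address the overall effect, and the tipping-point analysis addresses the pairwise comparisons with placebo.

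**Working it through.** **1. Count.** The subgroup factors in 3.10.2.5 are sex, age, race, BMI, diabetes, region, run-in blinding, home SBP, home DBP, number of BP medications, screening hypertension status and orthostatic hypotension: 12. The imputation model holds age, sex, race, BMI and home SBP: 5. Omitted: 12 − 5 = 7 (8 of 13 if the two hypertension cut-points are counted separately).

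**2. The plan's own figures.** With SD 11 and 100 vs 50, SE = 11 × √(1/100 + 1/50) = 1.905. Then 9/1.905 = 4.72 gives 99.7% power, and 13/1.905 = 6.82 gives 100.0%. Both match SAP 2.5. The SAP states no power for interactions. SAP 2.6.1 gives 295 randomized, which at 2:2:1 is 118/118/59.

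**3. Shrinkage by algebra.** Let a fraction f be missing in each arm and both levels, with the factor unrelated to the included covariates. Imputed values centre on the arm mean m whatever the level, so the level mean in the completed data is (1 − f)μ + f·m. The difference between levels within an arm becomes (1 − f) times its true value, and so does the interaction. A true 10 mmHg becomes 9.5, 9.0 or 8.0 at f = 5, 10 or 20%.

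**4. Simulation.** Inputs from the documents: 118 vs 59, SD 11, main effect 9 mmHg, two-sided 5%. Assumed: 30% prevalence of a binary factor, the interaction size and the missing rate. Within-arm regression imputation with Rubin's rules, 20 imputations, 600 replicates, no site clustering. Hand check with no missing data: SE = 11 × √(1/35.4 + 1/82.6 + 1/17.7 + 1/41.3) = 3.83, so a 10 mmHg interaction has about 74% power; the simulation gave 72 to 75%.

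| True interaction (mmHg) | Missing | Estimate: omitted / included | Rejection rate: omitted / included |
|---|---|---|---|
| 10 | 5% | 9.6 / 10.1 | 66% / 70% |
| 10 | 10% | 8.9 / 9.9 | 56% / 65% |
| 10 | 20% | 8.1 / 10.1 | 42% / 61% |
| 6 | 5% | 5.7 / 6.1 | 30% / 32% |
| 6 | 10% | 5.6 / 6.2 | 25% / 31% |
| 6 | 20% | 4.7 / 6.0 | 14% / 27% |
| 0 | 5 / 10 / 20% | about 0 | 4.0, 2.5, 1.7% / about 5% |

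At 20% missing and a 10 mmHg interaction, Rubin's SE with the factor omitted averages 4.4 against an empirical SD of 3.3, which is why the test is conservative. The same test on observed values alone has power 71, 66 and 61% at 5, 10 and 20% missing, in line with imputation that includes the factor.

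**5. Lower rates.** A second design (40% prevalence, SD 9.5, interaction 8 mmHg, 15 imputations, 2000 trials) gave power omitted / included of 72 / 73% at 1% missing, 69 / 71% at 2%, 68 / 70% at 3%, 65 / 69% at 5% and 56 / 66% at 10%. Monte Carlo error is about 1 point here (√(0.65 × 0.35/2000) = 0.011) and about 2 points in step 4, so differences at 1 to 3% are barely distinguishable from noise.

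**6. Adjusted analysis.** With an omitted covariate of true coefficient 5 and a true treatment effect of −9, the estimated effect at 5, 10 and 20% missing was −9.07, −9.08 and −8.95 omitted, against −9.07, −9.09 and −8.98 included. Only the covariate's own coefficient shrank (4.7, 4.5, 4.0).

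**The case against.** The strongest reply is that little will be imputed under item 4. Table 3-2 computes a Week 4 average from a single valid reading in up to 7 days. Readings transfer automatically (Protocol Appendix 3), adherence to the measurement schedule is telemonitored (Protocol 10.2.8), and only people who adhered during run-in are randomized (Protocol 8.2.1). Item 4 is also only part of all missingness, whereas the simulations assign it the whole missing fraction. This stands: rates of 10 to 20% have no support in the documents, and those rows only show how the effect scales.

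It is also fair that an interaction of 8 mmHg is nearly the whole 9 mmHg design effect. At 4 mmHg and 5% missing, power is 21% omitted against 24% included, so the test is weak either way. Correlated covariates soften the shrinkage: at 20% missing, a correlation of 0.6 with baseline SBP reduces it to about 14%. And a conservative test creates no false subgroup claims.

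None of this removes the mismatch. It limits its size.

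A reader might infer that the adjusted sensitivity analysis is compromised too, because diabetes and number of treatments (2 of its 6 covariates) are also absent from the imputation. The documents do not support that: 3.10.2.4 reports only the treatment difference, which step 6 shows is essentially unchanged. A reader might also infer from the sample code, where treatment is only a main effect, that all 12 interactions shrink. The text of 3.10.2.6 specifies imputation within treatment group, and SAP 2.1 describes the code as an example, so the five included factors are not affected on that reading.

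**Conclusion.** The point holds for the treatment-by-subgroup tests on the seven omitted factors, and only for those. Estimates are pulled toward zero by at most about the fraction imputed under item 4, and the heterogeneity p-values are too large. The size depends on a missing rate, interaction sizes and subgroup prevalences that the documents do not give. Given how few readings a Week 4 value needs, a loss of a few power points or less is the likely range. The simulations assume values missing at random, a binary factor and no site clustering.

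The primary comparison and the adjusted treatment difference do not change materially, so this does not bear on the trial's main conclusion. It is a modest defect in pre-specified supportive analyses, worth correcting because the correction is cheap.

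**What to change.** Leave the primary imputation and the placebo-donor rules as they are. Add to SAP 3.10.2.5 that, for each subgroup analysis on a factor outside the imputation model, the item 4 imputation is repeated within treatment arm with that one factor added. Report the same interaction test on observed Week 4 values beside it. Where the factor is too sparse among the roughly 59 placebo participants, use the observed-value test alone.

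Factors should be added one at a time. Putting all seven into the primary imputation would strain the placebo arm, where the model already has eight factors.

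The cost is SAP wording and a little programming; the variables are already in the planned subgroup list. The downside is that forest-plot rows would rest on slightly different imputed datasets, which a footnote should say.

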3.10.2 Primary Efficacy Analysis

3.10.2.1 Definition – Home BP

Home seated systolic and diastolic measurements will be averaged as described in [Table 3-2](#) and the following endpoints will be derived:

- Average home SBP during the 7 days prior to Randomization and FU1/Week 4
- Average home DBP during the 7 days prior to Randomization and FU1/Week 4
- Average trough (i.e., measurement taken before morning dose) home SBP during the 7 days prior to Randomization and FU1/Week 4

Note that trough will be assumed to be any BP measure taken in the morning, as participants are instructed to perform the BP measurement prior to taking their daily medication.

Table 3-2 Definitions of Home Blood Pressure Derivations

Measure	Rules
Randomization and week 4 home BP	
• Defined as home BP in the week before randomization and FU visit 1 (Week 4).
Individual BP measurement	
• Each BP measurement must consist of valid SBP and DBP values (i.e. SBP>60 mmHg and <250 mmHg and DBP>40mmHg and <150mmHg). If valid SBP and DBP are not recorded, the entire measure will be discarded.• Home BP are expected on at least 4 consecutive days immediately prior to the trial visits (i.e., Week -1, Week 4) and on a single set day of the participant's preference in other weeks.
Grouping of measurements into sessions	
• Individual BP measurements must be grouped into 5-minute "sessions".• To group individual BP measurements into sessions, the start of a 5-minute period is at the time of the first measurement with all BP measurements in those 5 minutes being allocated to the single session.• A new session starts at the first BP measure encountered after the completion of an existing session.• If more than two measures are captured in a session then, as with three measures, the second and third measures will be flagged for use. The first and any measures after the third are ignored.• In the case of fewer than three BP measures in a session, all measures will be flagged for use.
Selection of a single session per half-day period	
• Each day is divided into two half-days – AM and PM.• If more than one session occurs in one period e.g., two sessions in the AM period of a given day, one session only will be selected for use using two prioritisation steps:
– Sessions containing three or more BP measures will be prioritised over those with two. Those with only one BP measure will be used as a last resort.– If the first step does not uniquely select one session for the period, the earliest session of those selected in the first step will be used.
Calculation of averages	
• To calculate an average, perform a simple, unweighted mean of the flagged BP measurements in the selected sessions for the period of

	
interest.
 
– At Randomization: A minimum of 6 measures (e.g. ≥ 2 sets of triplicate measures or ≥ 3 sets of duplicate measures) are expected, including at least 1 morning and 1 evening, each with ≥ 2 measures per protocol-specified eligibility criteria.– Post-Randomization: At least 4 consecutive calendar days (8 measurement sessions, 24 BP readings) were recommended.– Calculations: For all timepoints, calculations of averages will be performed if there is at least 1 valid BP measurement.• The home BP values for the purpose of Baseline, FU visit 1 Week 4 are averages (as defined above) up to 7 calendar days immediately preceding each in-clinic visit.
– Each of the up to 2 selected sessions per day (1 morning and 1 evening) may be included in the calculation.• Days with no valid measures reported will be excluded from the calculation (i.e., only days with SBP measurements recorded will be included in average).
--	---

In addition, for descriptive plots of SBP and DBP measurements post-randomization, weekly average BP will be computed where Week is defined in relation to the randomization date with Week 1 initiating on Day 1, the first treatment with randomized trial medication:

Week = (date of BP measurement – date of first dose of randomized treatment)/7
Week is rounded up to the nearest integer. Averages will otherwise be calculated in the same manner as described in [Table 3-2](#).

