3.5 General Methods

All data listings that contain an evaluation date will contain a relative study day. Two relative study days will be defined: Period 1 Relative Day (P1 Rel Day) and Post-Randomization Relative Day (PR Rel Day). For Period 1 Relative Day, pre-treatment (screening) and on-treatment (run-in and post-randomization) study days are numbered relative to the day of the first dose of single-blind placebo which is designated as P1 Day 1. The preceding day is P1 Day -1, the day before that is P1 Day -2, etc. Post-Randomization Relative Day will be numbered relative to the day of the first dose of the randomized medication which is designated as PR Day 1.

The planned treatment group for all participants in Period 1 is placebo. In Period 2, the planned treatment group is randomly assigned to be:

1. **Triple $\frac{1}{4}$ (GMRx2):** telmisartan 10 mg/amlodipine 1.25 mg/indapamide 0.625 mg
2. **Triple $\frac{1}{2}$ (GMRx2):** telmisartan 20 mg/amlodipine 2.5 mg/indapamide 1.25 mg
3. **Placebo**

All output will be incorporated into Microsoft Word or Adobe Acrobat PDF files, sorted and labelled according to the ICH recommendations and formatted to the appropriate page size(s).

Tables will be produced for appropriate demographic, baseline, efficacy and safety parameters. For categorical variables, summary tables of the number and percentage of participants within each category (with a category for missing data) of the parameter will be presented. For continuous variables, the number of participants, mean, median, standard deviation (SD), minimum and maximum values will be presented. Summarizations will be presented by treatment group and overall. For safety summaries, Period 1 (placebo run-in period) will be summarized separately from the randomized treatment period and follow-up. Efficacy summaries will not be created for Period 1.

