3.10.2.8 Descriptive figures

The following graphical displays are planned:

- Plot of the LS Mean home SBP with 95% CI derived from the MM for the primary analysis will be presented.
- Results from the tipping point analysis will be presented graphically.
- Forest plots of the LS Means, 95%CI and p-values for determining heterogeneity by subgroup will be presented.
- Descriptive plots to display the average weekly SBP post-randomization, where Week 1 begins at first treatment post-randomization, Week 2 begins at Day 8 of treatment post-randomization, etc.
- Descriptive plots to display the change in average weekly SBP from randomization through the Randomization Period. Randomization will be defined as the 7 calendar days prior to the Randomization clinic visit (Table 3-2). The Randomization Period will begin on the first day of randomized treatment and will extend until the earliest of: FU1/Week 4 visit, End of Study visit, or 7 weeks of post-randomized BP home measurements.

Plots may be presented for the treatment groups overall as well as by subgroups, as appropriate. Similar plots may be presented for home DBP, as appropriate.

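### The SAP's week formula for the descriptive home BP plots puts the first day of every treatment week into the previous week, against the SAP's own definition of the weeks

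*SAP*

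**What the plan says.** SAP 3.10.2.1 introduces the week variable for one purpose: "for descriptive plots of SBP and DBP measurements post-randomization, weekly average BP will be computed". It fixes the start of the count in words, "with Week 1 initiating on Day 1, the first treatment with randomized trial medication", and then gives the calculation: "Week = (date of BP measurement – date of first dose of randomized treatment)/7". The rounding rule follows: "Week is rounded up to the nearest integer".

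SAP 3.10.2.8 repeats the intended boundaries when it lists the figures. The weekly SBP plot is one "where Week 1 begins at first treatment post-randomization, Week 2 begins at Day 8 of treatment post-randomization, etc". A second figure uses the same weekly averages: "Descriptive plots to display the change in average weekly SBP from randomization through the Randomization Period". Similar plots for home DBP are allowed for.

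SAP 3.5 settles the day numbering. Post-randomization days are "numbered relative to the day of the first dose of the randomized medication which is designated as PR Day 1", so there is no Day 0 after randomization.

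**The concern.** The words and the formula define different weeks. A programmer who codes the formula and one who codes the description in 3.10.2.8 would draw different figures from the same data.

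The number of readings per week makes this more than cosmetic. Protocol 10.2.8 and Appendix 3 ask for four days of readings before the randomization and Week 4 visits, but for a single set day in other weeks. For a participant who follows that schedule, an interim weekly value rests on one day, and no other day in the week dilutes a misplaced reading. If that day is the first of the week, the whole weekly value moves to the previous week. A Day 1 reading goes into a Week 0 that the SAP never defines. If the program did not restrict itself to post-randomization dates, Week 0 would also take in run-in Days -6 to -1.

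**Working it through.** **Inputs**
- Day of first randomized dose = Day 1 (SAP 3.5), so date difference = Day - 1.
- Week as written = the difference divided by 7, rounded up (SAP 3.10.2.1).
- Intended boundaries: Week 1 starts on Day 1 (SAP 3.10.2.1 and 3.10.2.8) and Week 2 on Day 8 (3.10.2.8). Continuing in sevens, Week 3 starts on Day 15 and Week 4 on Day 22.

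**Evaluating the formula, ceiling((Day - 1)/7)**

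| Day | Difference | Difference/7 | Week by formula | Week by the SAP's words |
|---|---|---|---|---|
| 1 | 0 | 0 | 0 | 1 |
| 2 | 1 | 0.14 | 1 | 1 |
| 7 | 6 | 0.86 | 1 | 1 |
| 8 | 7 | 1 | 1 | 2 |
| 9 | 8 | 1.14 | 2 | 2 |
| 15 | 14 | 2 | 2 | 3 |
| 22 | 21 | 3 | 3 | 4 |
| 28 | 27 | 3.86 | 4 | 4 |

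As written, the weeks are Day 1 = Week 0, Days 2-8 = Week 1, Days 9-15 = Week 2, Days 16-22 = Week 3 and Days 23-29 = Week 4. The stated boundaries are not reproduced.

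**Extent.** Over Days 1-28 the misplaced days are 1, 8, 15 and 22, and 4/28 = 14.3%, or one day in seven. Each is one week early.

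**Other readings of the rule**
- Rounding to the nearest integer puts Days 1-4 in Week 0 and Days 8 and 9 in Week 1, so it fails.
- Rounding down without adding 1 puts Days 1-7 in Week 0, so it fails.
- ceiling((difference + 1)/7), which equals floor(difference/7) + 1, gives Days 1-7 = Week 1, Days 8-14 = Week 2, Days 15-21 = Week 3 and Days 22-28 = Week 4. This matches the text.

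**Which scheduled readings are exposed.** Take a Week 4 visit 28 days after first dose, that is, on Day 29. The four scheduled pre-visit days are Days 25-28, which fall in Week 4 under either rule. Day 22 lies in the pre-visit week, when the schedule does not call for a single set-day reading. The set-day readings exposed at nominal timing are therefore mainly those of Days 8 and 15.

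**Share of participants.** The documents give no distribution of set days. If these were evenly spread over the week, 1 participant in 7 would be affected; with the 295 randomized (SAP 2.6.1), 295/7 is about 42. Without that assumption the share could lie anywhere from none to all.

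**The case against.** The case for leaving it alone has four parts.

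- **The intention is plain.** The boundaries are given in words twice, and a Week 0 appearing after randomization would probably be noticed in programming. This lowers the risk but does not remove the contradiction. Once Week 0 is noticed, relabelling it as Week 1 would cure Day 1 and leave Days 8 and 15 in the wrong week.
- **A morning reading is taken before that day's dose.** With dosing on schedule, a Day 8 morning reading reflects seven days of treatment, so plotting it under Week 1 is arguably a matter of labelling. This stands as a reason not to call the value misleading. It is not the definition the SAP gives, and it does not cover Day 8 evening readings.
- **Date-times might rescue Day 1.** With clock times an evening reading on the first dose day would round up to Week 1. The SAP specifies dates.
- **Most readings are right.** Six days in seven are placed correctly, and the size of any change in the plotted means has not been estimated in mmHg. Both statements are correct and limit the point.

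A reader might infer that Week 4 efficacy results are affected, since SAP 3.10.3.1 also speaks of weekly averaged home BP at Week 4. The documents do not support that. Table 3-2 builds the baseline and Week 4 values from up to seven calendar days before the corresponding clinic visit, without this formula. A reader might also extend the error to the home BP adherence counts. SAP 3.9.2 counts valid half-days by week of follow-up but neither cites the formula nor defines the week, so no error is shown there.

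**Conclusion.** The formula is wrong as written. It disagrees with SAP 3.10.2.1 and 3.10.2.8 on the first day of each week and agrees on the other six. The result follows from the SAP's own day numbering and needs no outside assumption.

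The consequence is small. It is confined to the descriptive weekly home BP plots, where the interim points for some participants would appear one week early. How many participants depends on set days chosen by preference, and the 1-in-7 figure is only an illustration under an even spread. It would be too strong to say that the plots are distorted, or that readings shift generally. No effect on the plotted means has been shown, and the primary estimate and the secondary Week 4 endpoints do not use the formula.

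**What to change.** In SAP 3.10.2.1, for the descriptive weekly plots, replace the formula with:

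Week = ceiling((date of BP measurement - date of first randomized dose + 1)/7)

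This gives Days 1-7 = Week 1 and Days 8-14 = Week 2, in line with SAP 3.5 and 3.10.2.8. The same edit should say how a Day 1 morning reading taken before the first dose is handled, because the corrected formula would place it in on-treatment Week 1.

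The cost is one added term and one clarifying sentence. No endpoint, sample size, data collection or trial procedure changes.
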